### **Other supporting studies/registries**

Title	Development of knowledge-based clinical decision support system for patients included in colorectal screening program
Registration number	2020-640-1
Start and End	Start: September 1, 2020 End: October 30, 2020
Publication	Lorenzo-Zúñiga V, Bustamante-Balén M, Pons-Beltrán V, Peña-Gil C. Development of knowledge-based clinical decision support system for patients included in colorectal screening program. Gastroenterol Hepatol. 2022;45(6):419-423. doi:10.1016/j.gastrohep.2021.05.01 (Lorenzo-Zuniga, Bustamante-Balen et al. 2022)
Design	Retrospective cohort study
Duration	2 months
Centres	Hospital Universitari I Politècnic La Fe- Valencia
Sponsor	Hospital Universitari I Politècnic La Fe- Valencia
Main objective	To develop a K-CDSS for the management of CRC screening patients, and to evaluate its efficacy.
Device investigation under	DILEMMA Solutions Platform® ( naevia medical)
Number of participants	69
Inclusion criteria	Patients at a large referral center in Spain who underwent colonoscopy under CRC screening program.
Exclusion criteria	Patients with a personal history of CRC, inflammatory bowel disease (IBD), hereditary polyposis syndromes, prior colectomy, Boston Bowel Preparation Scale (BBPS) < 5 or an endoscopic report of poor preparation quality (inadequate visualization of polyps < 5 mm), incomplete colonoscopy (defined as failure to intubate the cecum), and polyp retrieval failure.
Primary Outcomes	The degree of agreement between expert physicians and nurses using a CDSS based on colonoscopy data was very high. There were no differences in erroneous recommendations with PoliCare CDSS (Kappa value 1.0).

Dilemma Solutions S.L.	CHAPTER 06-1C	TD01-06-1C Ver.: 01 2025/03/03
	CLINICAL EVALUATION PLAN (CEP)	Page 35 of 38

Title	Development of knowledge-based clinical decision support system for patients included in colorectal screening program
Protocol reference	TD01-06-1C-06-06 CIP_2020-640-1

Title	Development and pre-clinical evaluation of an advanced decision support system for hypertrophic cardiomyopathy clinical management
Protocol code	2021-2-19-HCUVA
Publication	NA
Design	Observational, multicenter study for the validation of a digital clinical decision support tool (CDSS) applied to clinical cases of patients with hypertrophic cardiomyopathy.
Duration	9 months
Centres	Hospital Virgen de la Arrixaca
Sponsor	Amicus Therapeutics.
Main objective	To evaluate the degree of concordance between management decisions of experts (Standard Output) versus non-experts supported by the CDSS (non-experts+CDSS output), in patients with HCM.
Device investigation under	Naevia medical
Number of participants	4101 rules (algorithms) covering HCM and related problems (heart failure, atrial fibrillation, valvular heart disease, arterial hypertension, dyslipidaemias, diabetes, coronary syndromes) were coded in the CDSS and were evaluated in 60 cases (internal validation).
Inclusion criteria	Patients evaluated consecutively with a main diagnosis of hypertrophic cardiomyopathy in which the available clinical information is considered sufficient for the generation of diagnostic and therapeutic recommendations.
Exclusion criteria	Absence of relevant clinical information for medical decisions. Problems for case anonymization.
Primary Outcomes	External validation phase 1: For each question (n=42), the experts (n=10) provided a total of 56 answers (28 with and 28 without CDSS) and non-experts (n=9) provided 62 answers (31 with and 31 without CDSS), to sum a total of 2184 individual questions (42 per case in 26 cases evaluated twice) and 4956 answers (including 248 answers that were considered the references, and 4708 answers to be evaluated). In experts, the number of right answers improved with CDSS from 1020 to 1032 (1.1%) and the number of wrong answers decreased from 156 to 144 (7.6%) (p=0.46). In non-experts, the number of right answers improved from 1074 to 1094

Dilemma Solutions S.L.	CHAPTER 06-1C CLINICAL EVALUATION PLAN (CEP)	TD01-06-1C Ver.: 01 2025/03/03
		Page 36 of 38

Title	Development and pre-clinical evaluation of an advanced decision support system for hypertrophic cardiomyopathy clinical management
	
(1.9%) and the number of wrong answers decreased from 228 to 208 (8.7%) (<math>p=0.29</math>). External validation phase 2: 21 additional cases were evaluated by 4 experts (2 with, 2 without CDSS) and 4 non-experts (2 with, 2 without CDSS). The answers showed low concordance both inter and intra group, with and without CDSS (<math>\kappa < 5</math> for all evaluated answers).

Protocol reference	TD01-06-1C-06-01 CIP_2021-2-19-HCUVA

Additionally, Naevia Medical's platform has been or is being used in other significant registries, such as:

- The "REDMIO20: Spanish Registry of Dilated Cardiomyopathy due to RBM20 Gene Mutation," a multicenter registry coordinated by [name] from the Salamanca University Assistance Complex, which included 168 cases up to December 11, 2023.
  - o Protocol reference: *TD01-06-1C-06-03 CIP\_REDPMIO*
- The "PROceso asistencial integrado de Estenosis Aórtica grave Sintomática (PROCEAS)" 2020/405 registry, led by [name] from the Santiago de Compostela University Clinical Hospital, with 991 cases of aortic stenosis registered up to December 11, 2023.
  - o Protocol reference: *TD01-06-1C-06-04 CIP\_PROCEAS*

### Ongoing Clinical Investigations

- **Preliminary Study on Ischemic Heart Disease:** This study focuses on the "2023 ESC Guidelines for the management of acute coronary syndromes". As a result of an agreement with the European Society of Cardiology, simulations of 731 cases have been created up to December 11, 2023, along with 22 representative cases. This study is especially important to validate the system's capability in managing patients with ischemic heart disease, a highly prevalent area in cardiovascular medicine.
  - o Protocol reference: *TD01-06-1C-06-08 CIP\_ESC Guidelines. Preliminary Study on Ischemic Heart Disease*
- **Case registry and quality indicators in cardiac rehabilitation centers:**
  - o Protocol reference: *TD01-06-1C-06-05 CIP\_ReCardio.*

Dilemma Solutions S.L.	CHAPTER 06-1C CLINICAL EVALUATION PLAN (CEP)	TD01-06-1C Ver.: 01 2025/03/03
		Page 37 of 38

### **Future investigations / PMCF**

PMCF Studies will be performed with the aim of potentially widen the indications of Naevia medical.

- **Preliminary Study on Breast Cancer:** Studies based on the "ESMO Clinical Practice Guidelines for diagnosis, treatment, and follow-up" for early breast cancer have been conducted. This study is crucial to ensure that the Naevia Medical system can effectively manage breast cancer cases, following the established clinical guidelines.
- **Diabetes Mellitus:** Validation study for the management of type 2 diabetes: Based on the ADA (American Diabetes Association) guidelines.

### **Active Vigilance and Monitoring**

After the device is placed on the market, strategies, and methods to systematically collect, summarize, and assess post-market clinical data shall be defined in the specific Post-market Surveillance (PMS) plan, as well as in the Post-market Clinical Follow-up (PMCF) Plan.

The purpose is to proactively collect and evaluate clinical data from the use in humans of the device within its intended purpose with the aim of confirming the safety and performance throughout the expected lifetime of the device, of ensuring the continued acceptability of identified risks and of detecting emerging risks based on factual evidence.

Feedback information from PMS and PMCF shall be evaluated to determine any necessary product changes or improvements.

The impact of any proposed changes or improvements shall be reviewed and considered in the annual Risk Management and Clinical Evaluation reviews. Also, design changes shall be evaluated for impact on the Certificate(s) issued by the Notified Body. All such changes shall be controlled and documented updating the corresponding sections of this Technical Documentation.

Dilemma Solutions S.L.	CHAPTER 06-1C CLINICAL EVALUATION PLAN (CEP)	TD01-06-1C Ver.: 01 2025/03/03
		Page 38 of 38

### **Brief Summary**

The study aims to validate naevia medical, a knowledge-based clinical decision support system (CDSS), for clinical benefit and safety in cases of cardiac valvulopathies. Using a series of retrospective clinical cases of heart valve disease, the research will evaluate the number of appropriate and inappropriate recommendations during baseline measurement (conventional management) and after CDSS activation.

### Statistical analysis plan

The study is designed as a pre-test-post-test evaluation of a randomly assigned group, using a longitudinal repeated measures approach and retrospective validation. The clinical management of the included cases will be retrospectively evaluated by a panel of 3 experts with access to the most updated guidelines. For each case, the panel will perform the assessment at baseline (without CDSS) and repeated the assessment after the activation of the CDSS. The experts will label all the given clinical recommendations as appropriate or inappropriate and will identify the ones that are missing but relevant for clinical decision making. Finally, they will state their grade of agreement with the CDSS suggestions on a five-level Likert scale. The number and percentage of appropriate, inappropriate and missing relevant recommendations in each scenario will be considered for analysis.

### **Analysis of the amount and quality of recommendations**

The impact of the CDSS activation on the recommendations will be assessed by analyzing the *number* of recommendations (appropriate, inappropriate, missing) per patient. The mean number of appropriate, inappropriate, and missing relevant recommendations generated per patient will be compared before and after the CDSS activation. Descriptive statistics, including mean (standard deviation [SD]), median (interquartile range [IQR]), and range, will be reported for these counts. To statistically compare the distributions of the *number* of appropriate, inappropriate, and missing recommendations per patient before and after CDSS implementation, the Wilcoxon signed-rank test will be applied.

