	43(7), https://doi.org/10.1093/eurheartj/ehab395	561-632.		
Appropriate recommendations	Increase the number of appropriate recommendations by a factor of three	Clinical	-	An observational study consisting on a clinical validation of a CDSS applied to retrospective clinical cases of cardiac patients with valvular heart disease, shall confirm an increase in the number of appropriate recommendations by a factor of three over the recommendations generated with conventional management without the support system.
Inappropriate recommendations	Reduction of inappropriate recommendations	Clinical	-	An observational study consisting on a clinical validation of a CDSS applied to retrospective clinical cases of cardiac patients with valvular heart disease, shall confirm that Naevia medical, compared to conventional management, is able to significantly decreased the number of inappropriate and missing recommendations in all the domains analyzed.

Dilemma Solutions S.L.	CHAPTER 06-1C	TD01-06-1C Ver.: 01 2025/03/03
	CLINICAL EVALUATION PLAN (CEP)	Page 27 of 38

Concordance between expert evaluators	Professionals agreement [reference to sources]  *Joshi, A., S. Kale, S. Chandel and D. K. Pal (2015). "Likert Scale: Explored and Explained." Current Journal of Applied Science and Technology 7: 396-403.	Clinical	
 
- The panel's agreement with the CDSS was very high, with a mean Likert scale score above 4 in all domains (STD: 4.53, LTD: 4.68, CMT: 4.58, ITI: 4.62). The probability of strongly agreeing was significantly higher than the probability any of the other categories (z.ratio (5 1)= 30.88, p-value< 0.001, z.ratio (5 2)= 31.67, p-value < 0.001, z.ratio (5 3) = 30.21, p-value< 0.001, z.ratio (5 4)= 22.54, p-value< 0.001).
 
-
 

Safety of Naevia medical			

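### The SAP compares per-patient totals only, so new inappropriate and lost appropriate recommendations cannot be separated from net change, and the Table 1 safety question has no analysis

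*SAP*

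**What the plan says.** The SAP section headed Statistical analysis plan describes data at the level of the single recommendation: "The experts will label all the given clinical recommendations as appropriate or inappropriate and will identify the ones that are missing". This is done once at baseline and again after activation. The same section adds two quantities: "The number and percentage of appropriate, inappropriate and missing relevant recommendations in each scenario will be considered for analysis", and a rating in which "they will state their grade of agreement with the CDSS suggestions on a five-level Likert scale".

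The next SAP section, Analysis of the amount and quality of recommendations, reduces the labels to one total per category, patient and assessment: "The mean number of appropriate, inappropriate, and missing relevant recommendations generated per patient will be compared before and after the CDSS activation". The descriptive results are the mean with SD, and "median (interquartile range [IQR]), and range, will be reported for these counts". For inference, the totals are compared "before and after CDSS implementation, the Wilcoxon signed-rank test will be applied".

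In Protocol Section 11, Table 1, the row on inappropriate recommendations requires the study to confirm that the device "is able to significantly decreased the number of inappropriate and missing recommendations in all the domains analyzed". A later row of the same table, on recommendations that could lead to a serious adverse event, sets a different task. The study must determine whether the device, on real cases, gives inappropriate recommendations that endanger patients, and omission of a critical recommendation is included in that definition. The SAP does not mention this task.

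**The concern.** A decision-support device can fail in two ways that conventional care did not: it can give a wrong recommendation the clinicians did not give, or drop a right one that they did. Both are changes in particular items. A difference of totals shows only the balance of removals and additions within a category.

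A case that loses one clinician error and acquires a different device error has a difference of 0 and adds nothing to the signed-rank statistic. A case that goes from 3 inappropriate items to 2 counts as improved even if both remaining items are new. The planned results therefore cannot distinguish a device that corrects errors from one that partly replaces them. The Table 1 safety row depends on individual items, and the SAP gives it no table, listing or estimate.

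**Working it through.** **Inputs.** The number of cases, 101, is in the main-investigation table of Protocol Section 14. The test and summaries are those of the SAP. The documents give no baseline counts for this study and no figure on this point to reproduce, so every event count below is an assumption. The SAP states no significance level; two-sided 0.05 is assumed where one is needed. Zero differences are dropped, the usual handling.

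**Step 1: two devices, one planned result.** In both, 80 of 101 cases have one inappropriate item at baseline and 21 have none.

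- Device A clears 60 of these cases and leaves the same item in the other 20. New items: 0.
- Device B clears 60 and, in the other 20, removes the clinician's item and gives a different inappropriate one. New items: 20.

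| | Device A | Device B |
|---|---|---|
| Baseline mean | 80/101 = 0.79 | 0.79 |
| Mean after activation | 20/101 = 0.20 | 0.20 |
| Differences | 60 of -1, 41 of 0 | 60 of -1, 41 of 0 |
| Signed-rank z | 60/√60 = 7.75 | 7.75 |
| p | 9.5e-15 | 9.5e-15 |
| Cases with a new inappropriate item | 0 | 20 (19.8%) |

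When all non-zero differences have size 1, the ranks are tied and z reduces to (number of -1 minus number of +1)/√(number non-zero). The distribution of counts at each assessment is the same for A and B, so the SD, median, IQR and range also agree. Only the last row differs, and the SAP does not plan it. The exact (Clopper-Pearson) 95% interval for 20/101 is 12.5% to 28.9%.

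**Step 2: new items in other patients.** Suppose 40 cases lose one item and 20 different cases gain one. The mean goes from 40/101 = 0.40 to 20/101 = 0.20, z = (40 - 20)/√60 = 2.58 and p = 0.0098. Nothing is masked within patients here: the 20 new items are 20 adverse ranks and make up the whole post-activation total. The planned summaries still do not say that 20 patients got worse or that the items are new.

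**Step 3: lost appropriate items.** Suppose a case has 4 appropriate items at baseline and 12 after activation, with no overlap. The count triples (12/4 = 3) although all 4 clinician items are gone. If the panel judges all 16 relevant, the 4 lost items should be labelled missing after activation, so the loss does reach a planned count. That count is also a net one: missing goes from 12 at baseline to 4 after, which reads as improvement, and nothing identifies the 4 as losses.

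**Step 4: mixed patterns.** A simulation used 101 cases, 2000 runs, Poisson inappropriate counts with baseline mean 1.0, and a post-activation mean held at 0.5.

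| Share removed / new items per patient | New items | Cases with a new item | of these, net worse | of these, net equal or better | Significant reduction |
|---|---|---|---|---|---|
| 50% / 0 | 0 | 0 | 0 | 0 | 100% |
| 60% / 0.1 | 10 | 10 | 5 | 4 | 100% |
| 80% / 0.3 | 31 | 26 | 13 | 13 | 100% |
| 100% / 0.5 | 50 | 40 | 18 | 22 | 98% |

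Entries are rounded averages. The same fall in means is compatible with 0 to about 40 of 101 cases having a new inappropriate item. Roughly half of the affected cases appear as adverse differences; the rest do not.

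**The case against.** A reader might infer that new errors never appear in any planned result, or that they are cancelled by gains elsewhere. The documents do not support either reading.

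- Post-activation totals of inappropriate and missing items are reported in their own right. In Step 1 the 20 items are in the table for both devices; what is absent is whether they are new.
- The three categories are analysed separately. A new inappropriate item can be offset only by a removed inappropriate item, not by extra appropriate ones.
- A net-worse patient is an adverse rank, and a lost relevant item should be picked up as missing.
- Protocol Table 1 does pose the safety question, and the Likert item has the panel judge the device's suggestions directly.

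These points stand, and they limit the concern. They do not remove it. A total does not separate new items from persisting ones. An adverse rank feeds a test statistic, and the SAP does not plan to report how many patients worsened. The Likert rating has no comparison with baseline. Table 1 asks a question that the SAP leaves without an analysis.

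It can also be said that the documents leave open what the post-activation assessment covers. If it covers device output alone, every inappropriate item in it was issued by the device, and the total already gives the device's error burden. If suggestions are added for a physician to accept or reject, as Protocol Section 4 describes use, loss of clinician items is less likely. Either way, the total does not show which errors conventional care had not made.

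Finally, nothing in the documents says recommendations are coded so that they can be matched, so the remedy takes some work.

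**Conclusion.** The concern holds in a limited form. The SAP analyses per-patient totals within each category and specifies no analysis for the Table 1 question on unsafe recommendations and critical omissions. New inappropriate items cannot be told from persisting ones, lost appropriate items cannot be told from other missing ones, and within-patient exchanges are fully masked.

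That the totals cannot separate these patterns follows from the plan's structure and needs no assumption about rates. The size does: under the assumed counts, identical planned tables arise with 0 or with 20 of 101 cases (19.8%) carrying a new error, and in the simulation the range is 0 to about 40. None of these figures predicts what the study will show. The net comparison remains a valid answer to whether totals changed; it is incomplete for the safety claim.

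**What to change.** In the SAP section on the amount and quality of recommendations, add a descriptive item-matched analysis of the labels already collected:

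- State the matching rule (when two recommendations in the same case count as the same item, and who decides in doubt) and what the post-activation assessment contains.
- Classify inappropriate items as removed, persisting or new, and appropriate items as kept, gained or lost.
- Report the number and proportion of the 101 cases with at least one new inappropriate item, and with at least one lost appropriate item, with exact 95% intervals.
- List new or omitted items that meet the safety definition in Protocol Section 11, Table 1.
- Show these results beside the net counts wherever the Table 1 claims on inappropriate recommendations and on safety are made. No new pass/fail threshold is needed; the documents offer no basis for one.

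The cost is SAP wording and matching work for 101 cases, probably with some adjudication, and no new patients or ratings. The safety figure may look less favourable than the net count. The Protocol dates the study to 2024 and already gives panel agreement results, so if the labels have been seen, the analysis should be marked as added afterwards.

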### Main clinical investigation

Title	Clinical validation study of naevia medical, a decision support tool for valvular heart disease
Registration number	ClinicalTrials.gov ID NCT06392464
Start and End	2024
Publication	Pending
Design	pre-test-post-test of a randomly assigned group, using a longitudinal repeated measures approach and retrospective validation
Duration	3 months
Centres	Instituto de Investigación Sanitaria de Santiago de Compostela (IDIS)
Sponsor	DILEMMA SOLUTIONS SL
Main objective	Demonstrate that the use of the naevia medical CDSS significantly increases appropriate recommendations based on clinical practice guidelines, and decreases the number of inappropriate recommendations received by the patient, compared to conventional management.
Device investigation under	Naevia medical
Number of participants	101

Dilemma Solutions S.L.	CHAPTER 06-1C CLINICAL EVALUATION PLAN (CEP)	TD01-06-1C Ver.: 01 2025/03/03
		Page 33 of 38

Title	Clinical validation study of naevia medical, a decision support tool for valvular heart disease	
Inclusion criteria	
Retrospective clinical retrospective cases of patients with valvular heart disease will be selected in a stratified randomised manner from among:
 
 
(i) patients presented at a medical-surgical session.
 
ii) patients from the monographic consultation of valvopathies.
 
 
Inclusion criteria:
 
 
- Clinical cases of patients randomly selected from among those presented during the year 2022 in medical-surgical session with the main diagnosis of aortic valvular stenosis, aortic insufficiency, mitral stenosis and mitral insufficiency (greater than moderate grade). Randomisation will be stratified ensuring that 50% come from the medical-surgical session.
 
- Clinical cases of patients randomly selected from clinical records of the Valvopathy Consultation seen in 2022 with the main diagnosis of aortic stenosis, aortic insufficiency, mitral stenosis and mitral insufficiency (major degree).
 
mitral regurgitation (greater than moderate grade). Randomisation will be stratified by ensuring that at least 40% of patients have aortic valve disease and 20% have mitral valve disease.
 
- Age <math>\geq 18</math> years.
 
	

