Exclusion criteria	
 
- Subjects under 18 years of age.
 
- Inability to anonymise the case.
 
- Clinical cases of valvular heart disease involving complex congenital heart disease.
 
- Clinical cases that do not meet the minimum set of data necessary for decision-making.
 
- Clinical cases with a principal diagnosis other than valvular heart disease.
 
- Presence of bacterial endocarditis.
 
	
Primary and Secondary Outcomes	
It is considered clinically beneficial to increase the number of appropriate recommendations by 15% over the recommendations generated with general management without the support system.
 
The baseline/pre-test value is the number of appropriate recommendations based on clinical practice guidelines during conventional management (without CDSS). Inappropriate recommendations as judged by the committee of expert assessors during conventional management will also be collected.
 
The post-intervention/post-test value is the number of appropriate guideline-based recommendations after activation of the naevia medical decision support system. Inappropriate recommendations in the judgement of the committee of assessors during CDSS management will be collected.
 
To calculate the percentage increase between two values we will use the following formula:
 $\text{Percentage increase} = (\text{Post-intervention value} - \text{Baseline value}) / \text{Baseline value} \times 100$	

Dilemma Solutions S.L.	CHAPTER 06-1C	TD01-06-1C Ver.: 01 2025/03/03
	CLINICAL EVALUATION PLAN (CEP)	Page 34 of 38

Title	Clinical validation study of naevia medical, a decision support tool for valvular heart disease
	value) ×100%.
Protocol reference	TD01-06-1C-06-02 CIP_NCT06392464

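### Three unranked signed-rank tests and three conflicting success rules let the same result be called a success or a failure

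*SAP*

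**What the plan says.** The SAP (Analysis of the amount and quality of recommendations) counts three kinds of recommendation per patient, before and after CDSS activation. It describes them with summary statistics and then states that, for the numbers "of appropriate, inappropriate, and missing recommendations per patient before and after CDSS implementation, the Wilcoxon signed-rank test will be applied". It names no primary contrast, alpha, sidedness, order, multiplicity rule or criterion for a positive study, and labels none of the three comparisons exploratory.

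The Protocol touches on success in three places:

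- **Section 14, Main clinical investigation, Main objective.** The study is to show that the CDSS "significantly increases appropriate recommendations based on clinical practice guidelines, and decreases the number of inappropriate recommendations received by the patient". Missing recommendations are not mentioned.
- **Section 14, same table, Primary and Secondary Outcomes.** The row does not say which outcome is primary. It states: "It is considered clinically beneficial to increase the number of appropriate recommendations by 15" per cent. It then adds: "Inappropriate recommendations as judged by the committee of expert assessors during conventional management will also be collected". A percentage-change formula follows, tied to no test or confidence limit.
- **Section 11, Table 1.** One row requires a threefold increase in appropriate recommendations. The next requires confirmation that the device "is able to significantly decreased the number of inappropriate and missing recommendations", and extends this to every domain analysed.

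Section 7 repeats the all-domains expectation for inappropriate and absent recommendations, and section 7.1 repeats the factor of three. No passage says which rule governs.

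**The concern.** A confirmatory claim needs a rule, fixed in advance, that sorts every possible result into success or failure. Here the SAP adopts none of the three Protocol rules, and those rules disagree on results that could well occur. Someone holding the finished tables could pick the rule that fits.

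The disagreement bears on safety as well as benefit. Table 1's final row lists inappropriate recommendations that may endanger patients, and counts omission of critical recommendations among the risks. Both the inappropriate and the missing counts are therefore relevant to safety. Under the outcomes row alone, success could be declared whatever happened to either of them.

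**Working it through.** **Inputs from the documents.** 101 cases (Protocol section 14); three signed-rank tests (SAP); thresholds of 15% and a factor of three (Protocol section 14 outcomes row; section 11 Table 1). Neither document gives an alpha, power, standard deviation or expected count, so the figure of 101 cannot be reproduced. Two-sided 0.05 is assumed below.

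**Step 1. Put the thresholds on one scale.** With the Protocol's formula, (post − baseline)/baseline × 100:
- a 15% increase is a ratio of 1.15;
- a factor of three is a ratio of 3, or (3 − 1)/1 × 100 = 200%.

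Any ratio from 1.15 to below 3 meets the outcomes row and fails Table 1. For example, a mean of 4 rising to 6 per case is (6 − 4)/4 × 100 = 50%.

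**Step 2. Apply the rules to the same results.**

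| Result | Outcomes row | Main objective | Table 1 |
|---|---|---|---|
| Appropriate significantly up, ratio 1.5; inappropriate not lower | met | not met | not met |
| Appropriate significantly up, ratio 1.5; inappropriate significantly lower | met | met | not met |
| Appropriate significantly up, ratio 4; inappropriate not lower | met | not met | not met |

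**Step 3. Illustrate how often the rules part.** The simulation used 101 paired Poisson counts with gamma patient frailty (shape 4), signed-rank tests with zeros dropped, and two-sided 0.05 in the claimed direction. Mean counts are assumptions, and the three counts were simulated independently. Appropriate rises from 3 to 4, a ratio of 1.33.

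| Inappropriate mean | Appropriate significantly up | Both significant | Appropriate significant, inappropriate lower in direction only |
|---|---|---|---|
| 0.5, unchanged | about 96% | about 3% | about 45% |
| 0.5 to 0.8 | about 96% | about 0% | about 0% |
| 0.5 to 0.3 | about 96% | about 55% | about 94% |

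The first row agrees with simple arithmetic. With no true change in inappropriate items, a significant fall has probability 0.025, and 0.96 × 0.025 = 0.024. The two right-hand columns are two readings of the main objective, whose adverb attaches clearly only to the increase. The 96% is for significance, not for the 15% threshold.

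A second simulation applied the thresholds themselves. It assumed baseline means of 4 appropriate, 0.5 inappropriate and 3 missing, with missing falling by 60%, pooled over domains. At a true ratio of 1.5 with inappropriate unchanged, the 15% rule was met in 100% of runs, joint significance in 3.5% and the factor of three in 0%. With inappropriate halved, the figures were 100%, 82% and 0%.

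**Step 4. False-positive rate, by rule.**
- Any one of three tests may be claimed: 1 − 0.95³ = 0.143 if independent. At correlations of 0.3, 0.5 and 0.8 it is 0.136, 0.125 and 0.098.
- All named contrasts must succeed: no inflation; the cost is power. With 90% power per test and independence, joint power is 0.9² = 0.81 for two tests and 0.9³ = 0.73 for three. For eight tests (inappropriate and missing in each of the four domains named in section 7.1) it is 0.9⁸ = 0.43.

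**The case against.** The best defence is that these statements sit at different levels. Table 1 is titled as an indicative list of acceptance parameters for the device, and the 15% reads as a threshold of clinical relevance. The trial's own rule may stand in the clinical investigation plan cited at the end of the section 14 table, which was not supplied. That limits the finding to the two documents in hand. It does not remove it: Table 1 says this kind of study shall confirm its criteria, and the SAP points to no other document for a rule.

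One could also say that appropriate recommendations are the implied primary outcome, since only they have a threshold in the outcomes row. No passage says so, and the main objective adds inappropriate recommendations.

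Four stronger readings are tempting, and the documents do not support them:

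- **That the study has a false-positive rate of 0.10 to 0.14.** This needs a rule allowing any one of three tests to be claimed. No passage states one, and the main objective reads as a joint requirement.
- **That inappropriate recommendations are the only tested outcome bearing on safety.** Table 1 counts critical omissions as a safety risk, and the SAP tests missing recommendations.
- **That more appropriate items with no fall in inappropriate ones is the likely result.** This is an assumption. The hypertrophic cardiomyopathy study in section 14 shows wrong answers falling from 156 to 144 and from 228 to 208, neither significantly.
- **That a rule was chosen after the results were seen.** The plan is dated 2025/03/03, dates the study 2024, and already reports panel agreement in section 7.1. It therefore cannot show that the rules came first, but it does not show that they came later.

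**Conclusion.** The concern holds for the two supplied documents. Three tests stand unranked, and the Protocol's success rules are incompatible. The firmest part needs no assumptions: every appropriate ratio from 1.15 to below 3 meets the outcomes row and fails Table 1, and a rise of at least 15% with no fall in inappropriate items meets the outcomes row and fails the other two.

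The simulated frequencies illustrate the gap and are not predictions. They rest on assumed means and independent counts, although appropriate and missing counts are plausibly linked. They also depend heavily on whether the main objective requires a significant fall in inappropriate items: about 3% against about 45% when the true mean is unchanged. Inflation of type I error is conditional on a rule the documents do not contain.

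**What to change.** State one success rule in the SAP section on the amount and quality of recommendations, and align the main objective, the outcomes row and Table 1 with it. A wording that follows the sponsor's main objective:

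> The co-primary contrasts, per patient, are the increase in appropriate and the decrease in inappropriate recommendations with the CDSS versus baseline. Each is tested at two-sided 0.05, and the study is positive only if both are significant in the stated direction. Missing recommendations are the key secondary outcome, tested at two-sided 0.05 only if both co-primary contrasts succeed.

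Two further decisions are needed, or the conflict survives:

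- Choose either 15% or a factor of three for appropriate recommendations, and judge it by a confidence limit on the ratio. The signed-rank test addresses no change, not either threshold. A point estimate is a weak rule: in the second simulation, a true ratio of exactly 1.15 reached the 15% mark in 47% to 50% of runs.
- Say whether Table 1's all-domains condition is confirmatory. The SAP describes no analysis by domain.

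If any of these results were known before the rule is written, it cannot be presented as pre-specified. In that case report all three tests with Holm-adjusted p-values and state that the order was not fixed in advance. If the clinical investigation plan already names a primary outcome, carry it into the SAP and reconcile the Protocol passages with it.

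The cost is amended text in both documents and a ratio analysis; no new cases are needed. The drawback is that a positive result becomes harder to claim, because a failed co-primary contrast can no longer be passed over.
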